#### **10.4. Background and Demographic Characteristics**

Subjects' age, height, weight, and continuous baseline characteristics will be summarized using descriptive statistics, while gender, race, and other categorical variables will be summarized using frequency tabulations. Medical history data will be summarized using frequency tabulations by system organ class and preferred term.

#### **10.5. Subject Disposition**

For all enrolled subjects, disposition will be summarized by ITT, Safety, and EE population. Reasons for treatment termination will be summarized for all enrolled subjects according to the treatment termination reason collected in the eCRF. A summary of subjects enrolled by site will be provided. Protocol deviations will be summarized using frequency tabulations.

#### **10.6. Efficacy Analysis**

The primary efficacy analysis will be performed on both the ITT and EE populations. The exact binomial test will be used to test the hypothesis that the ORR for the Cohort A is greater than 16%. The final primary analysis on ORR will report exact 2-sided p-values with 95% Clopper-Pearson confidence intervals (Collett, 2003). For Cohort B point estimates of the ORR together with 95% confidence interval will be calculated using the normal approximation to the binomial distribution. Analysis for Cohort C will mirror the analysis for Cohort A except for a test of the hypothesis of an ORR greater than 25%.

The Kaplan-Meier procedures will be used to characterize the time-to-event curves (PFS, OS, TTP, and response duration) and the median and 95% confidence intervals of time to each of these events will be estimated. Univariate summary statistics will be provided for time to response. Progression-free survival and OS will be analyzed in the ITT as well as the EE populations. Other secondary efficacy endpoints will be analyzed in the ITT population only.

Analyses of PFS, OS, TTP, and response duration will be updated at the end of the long-term follow-up phase of the study.

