  - p Assessment/measurement at specified time-points only required if EMPs are present. If EMPs are clinically assessable, clinical assessment will be performed at screening, at every Cycle Day 1, and at treatment discontinuation. If EMPs are only assessable radiographically (x-ray and/or conventional [spiral] CT/MRI scan), scans are required at screening, at Cycle 3 Day 1, every 3 cycles thereafter (Cycle 6 Day 1, Cycle 9 Day 1, etc.) during treatment, at treatment discontinuation, and when clinically indicated to confirm response ( $\geq$  PR).
  - q A skeletal survey by x-ray will be performed at screening and when clinically indicated per the investigator's discretion. If a skeletal survey was performed within 60 days prior to the start of Cycle 1, it may be used for the screening assessment if approved by sponsor. Refer to [Appendix C](#) for detailed requirements.
  - r Response, including PD, will be assessed by investigators using the modified International Myeloma Working Group criteria ([Appendix B](#)). Response assessment should also be repeated at the time of response ( $\geq$  PR) or PD confirmation. The first response assessment will occur at Day 1 of Cycle 2.
  - s Subsequent anti-myeloma regimens: type of treatment, start and stop dates, date of progression and best response whenever possible.
  - t For Cohort A and Cohort B subjects who consent to participate in biomarker analysis may undergo collection of bone marrow aspirate and whole blood samples at screening, response assessment (confirm CR) and disease progression, and when clinically indicated. Additionally, whole blood samples will be collected at Day 1 of Cycle 3,5 and

treatment discontinuation for Cohort A and **C1D1, C1D8, C1D15, C2D1, C2D15, C3D1, C5D1 and treatment discontinuation** for Cohort B. For Cohort C, all subjects will provide bone marrow aspirate at screening and treatment discontinuation.

u For Cohort A and Cohort B subjects who consent to participate in biomarker analysis may undergo collection of normal tissue (which may include saliva samples) at screening only.

v For subjects enrolled in Cohort B, Quality of Life (QoL) measured with the descriptive system of the EQ-5D will be provided to each subject to complete on Day 1 of every cycle prior to any study treatment (POM, DARA, LD-dex) administration and at treatment discontinuation.

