#### **ITT Population**

The ITT population is defined as all enrolled subjects regardless of whether they received any of the study treatment. The ITT population will be used for all efficacy analyses.

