#### **Efficacy Evaluable (EE) Population**

This population will consist of all enrolled subjects who meet eligibility criteria, take at least one dose of study drug, and have at least one post-baseline response assessment. The EE population will be used to provide supporting sensitivity analyses for the primary endpoint and key secondary endpoints.

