#### **Progression-free Survival**

Progression-free survival will be calculated as the time from start of treatment until the time of PD (as determined by the site investigator based on the mIMWG criteria) or death from any cause on study treatment, whichever comes first. Subjects not experiencing a documented progression will be censored at the time of their last response assessment (or at the time of trial enrollment if no assessment was conducted).

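### PFS and OS in the EE set leave out subjects who die before any response assessment, which pushes these supportive curves upward

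*Combined protocol and SAP*

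**What the plan says.** Section 10.6 plans Kaplan-Meier curves and states that "Progression-free survival and OS will be analyzed in the ITT as well as the EE populations". Section 10.2 limits EE to enrolled subjects who are eligible, "take at least one dose of study drug, and have at least one post-baseline response assessment". On timing, footnote r of Table 1 says "The first response assessment will occur at Day 1 of Cycle 2". Section 6 (Assessment of Response) adds an assessment at the treatment discontinuation visit, which the Protocol Summary requires of everyone who stops treatment.

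The clock starts earlier. In Section 10.6, "Progression-free survival will be calculated as the time from start of treatment until the time of PD" "or death from any cause on study treatment, whichever comes first", and OS likewise runs from the start of treatment. The Protocol Summary (Overview of Efficacy Assessments) gives enrollment as the origin instead; both precede the first assessment. For PFS, subjects without documented progression are censored at their last assessment, "or at the time of trial enrollment if no assessment was conducted". Neither landmark nor delayed entry is described.

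On the roles of the sets, Section 10.2 says "The ITT population will be used for all efficacy analyses" and "The EE population will be used to provide supporting sensitivity analyses for the primary endpoint and key secondary endpoints".

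**The concern.** Membership of EE is settled by something that happens after time zero. A subject who dies before any response assessment is counted in ITT OS, and in ITT PFS if the death was on treatment, but is not in EE at all. The EE curves nevertheless start at time zero, as if everyone in the set had been at risk of exclusion-free follow-up from that point. This is immortal-time selection, and it acts in one direction: it raises the curves.

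What is at stake is the value of the sensitivity analysis. A supportive set should be able to show that the main result is fragile. One whose entry rule removes early deaths is poorly placed to do so. Section 10.6 also updates PFS and OS at the end of long-term follow-up, so the artefact would be carried into the later reports. For ORR the position is different: Section 10.6 counts unassessed subjects as nonresponders in the main analysis, so EE offers a recognizable contrast there.

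**Working it through.** The documents give no PFS or OS sample size, event count or expected median for this trial, so there is no stated figure to reproduce. The check is structural, followed by an illustration of size.

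**Inputs**

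- First scheduled assessment: Cycle 2 Day 1, about 28 days or 28/30.4375 = 0.92 month after the start of treatment (Table 1, footnote r).
- Cohort sizes: 112 enrolled in Cohort B and about 20 planned in Cohort C (Section 7.1).
- Illustrative medians, used only to size the effect: OS 14.4 months and PFS 4.6 months with pomalidomide plus low-dose dexamethasone in the sponsor's phase 1b/2 study, and OS 35.9 months in the alternate-day cohort of the phase 1b study (both Section 1.2).
- Share d who die before any assessment: not given. Assumed range 1% to 10%.

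**Step 1: OS inflation.** If the only difference between the sets is the removal of a share d who die unassessed, and nobody is censored before then, then after the first assessment

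S_EE(t) = S_ITT(t) / (1 - d) = S_ITT(t) × n/(n - k), for k such deaths among n.

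- Cohort C, k = 1: 20/19 = 1.053. With k = 2: 20/18 = 1.111.
- Cohort B, k = 4: 112/108 = 1.037.

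**Step 2: a plausible d.** With exponential survival and median m, d = 1 - exp(-0.92 × ln 2 / m), taking every death before Day 28 as unassessed.

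- m = 14.4: d = 4.3%, or 0.043 × 20 = 0.9 subject in Cohort C.
- m = 35.9: d = 1.8%, or 0.018 × 20 = 0.4 subject.

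**Step 3: effect on OS.** With m = 14.4 and d = 4.3%, 12-month OS is 56.1% in ITT and 56.1/0.957, about 58.7%, in EE. The EE median is 14.4 + 0.92 = 15.3 months (+0.9). For other d, the shift in the median is m × [-ln(1 - d)] / ln 2, with the exponential used only for the slope of the curve near its median:

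- d = 1%: 14.4 × 0.01005/0.693 = +0.2 month.
- d = 10%: 14.4 × 0.1054/0.693 = +2.2 months.

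**Step 4: effect on PFS.** The route is narrower. A progression needs an assessment, and a living subject without one is censored at time zero in ITT and so adds nothing to that curve. Only on-treatment deaths before any assessment make a difference, reading the death clause as overriding the censoring rule. With a median of 4.6 months the same formula gives +0.07 month at d = 1%, +0.3 at 4.3% and +0.7 at 10%. At d = 4.3%, 6-month PFS moves from 40.5% to 42.3%.

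**Step 5: simulation.** In 400,000 subjects with median OS 14.4 months, median time to progression 6 months, progression detected at 28-day visits, and no assessment before Day 28:

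| | ITT | EE |
|---|---|---|
| OS at Day 28 | 95.6% | 100% |
| OS at 12 months | 56.0% | 58.6% |
| Median OS (months) | 14.4 | 15.3 |
| PFS at Day 28 | 86.0% | 89.9% |
| PFS at 6 months | 39.5% | 41.3% |
| Median PFS (months) | 4.60 | 4.60 |

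The PFS median stays on the same visit date although the curve rises. Adding 5% or 10% living subjects without an assessment left PFS essentially unchanged. If 10% are such subjects and their survival times are halved, the OS medians are 13.4 months in ITT and 15.3 in EE, so the OS gap widens.

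**The case against.** A reader might infer that no EE subject can have an event in the first cycle, so that the EE curves are flat at 100% for four weeks. The documents do not support this. The required treatment discontinuation visit includes a response assessment, so a subject who stops early and is assessed there enters EE and can progress or die before Day 29. Cycle visits also have a window of 3 days either side. The 100% at Day 28 in the simulation follows from leaving out that earlier route.

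A reader might also infer that EE can only look better than ITT. That holds for this component alone. EE also drops ineligible subjects, whose effect on the curves has no known direction, so the EE curve as a whole could lie below ITT.

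On size, the 14.4-month median comes from subjects with a median of 5 prior therapies, whereas this trial enrolls after 1 or 2 prior lines. Two unassessed deaths among 20 is therefore the pessimistic end of the range, with no anchor in the documents.

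On consequence, EE is labelled supporting, ITT is reported beside it, disposition is summarized by population (Section 10.5), deaths within 28 days of the last dose are tabulated (Section 10.7), and PFS and OS carry no hypothesis test. All of this stands and limits the weight of the point. It does not remove the selection, because none of these provisions corrects the EE curves.

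**Conclusion.** The point holds in a limited form. Subjects who die before any assessment are removed from EE because of a post-baseline outcome, and the clock still starts at treatment. This component biases the supportive EE OS curve upward, and the EE PFS curve to a lesser extent, under either stated time origin. Agreement between EE and ITT is therefore weak reassurance for these two endpoints.

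The size is probably small and cannot be fixed from the documents. Over an assumed 1% to 10% of unassessed deaths, later EE OS is inflated by a factor of 1.01 to 1.11. With the illustrative medians, that is +0.2 to +2.2 months on median OS and +0.07 to +0.7 month on median PFS. These figures assume that no excluded subject was assessed at an early discontinuation visit, and they leave aside the ineligibility exclusions. The ITT results are unaffected, and no decision rule depends on the EE curves.

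**What to change.** In Section 10.6, replace EE for PFS and OS with a supportive set that does not depend on post-baseline assessment. The better choice is enrolled subjects who met eligibility at baseline and took at least one dose, whether or not a response was ever assessed. It keeps the useful check on ineligible enrollees. The safety population is also valid and already defined, but it differs from ITT only by subjects who were never dosed and so would nearly duplicate it.

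Make a matching edit to the EE definition in Section 10.2, so that its supporting role no longer extends to key secondary endpoints, and keep EE as defined for the ORR sensitivity analysis only.

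If EE curves for PFS and OS are kept, start them at a Cycle 2 Day 1 landmark among subjects still at risk then (alive for OS, alive and progression-free for PFS), and label them as conditional on reaching it.

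The cost is about one sentence in each section, with no change to data collection. The supportive curves may look slightly less favourable.

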### **Primary Efficacy Endpoint**

The primary endpoint will be the overall response rate (ORR) by mIMWG criteria and will be based on the best response prior to the data cut-offs. Data cut-offs for the primary endpoint for Cohort A are planned for 6 cycles after about 40% of the subjects enroll and 6 cycles after the last patient enrolls. For Cohort B and Cohort C the primary endpoint may be assessed at time points allowing for early dissemination of descriptive results, after the last subject is enrolled, and after adequate follow up of all subjects enrolled. The ORR will consist of the responses of PR or better (CR, VGPR, or PR). A response that is documented after the initiation of another anti-myeloma treatment will not be counted as a response. However, these subjects will be included in the denominator for the ORR calculation. Subjects without an assessment of response will be considered nonresponders.

### **Secondary Efficacy Endpoints**

#### **Time to Response**

Time to response, calculated for responders only, is calculated as the time from the start of treatment to the first documented response (PR or better) based on mIMWG criteria.

#### **Duration of Response**

Duration of response, calculated for responders only, is defined as time from the initial documented response (PR or better) to the first confirmed PD or until death from any cause. Subjects without documented progression will be censored at the time of their last response assessment.

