#### **Time to Progression**

Time to progression will be calculated as the time from start of treatment until PD (as determined by the site investigator based on the mIMWG criteria). Subjects not experiencing a documented progression will be censored at the time of their last response assessment (or at the time of trial enrollment if no assessment was conducted).

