## 1. JUSTIFICATION FOR AMENDMENT

Significant changes included in this amendment are summarized below:

- Section 7. STUDY POPULATION. Protocol is amended to enroll subjects in North America which includes United States and Canada.

The amendment also includes other clarifications and corrections.

- Section 5. TABLE OF EVENTS Updated (page 28-31)
- Section 6. PROCEDURES, Study Entry, (page 32). Corrected sentence in second paragraph, first sentence. “...[Appendix H], medical history, ...”
- Section 6. PROCEDURES, Estimation of Renal Function, (page 34). Added “only” after Screening and deleted “...on Day 1 of every cycle, and at treatment discontinuation.”
- Section 6. PROCEDURES, Exploratory Biomarker Study, (page 37). Added to paragraph starting with “Whole blood sample...” “...at treatment discontinuation (disease progression)...”
- Section 10.6 Efficacy Analysis, Duration of Response (page 48). Added “...or until death from any cause.” to the end of the first sentence.
- Section 10.6 Efficacy Analysis, Time to Progression (page 48). Deleted “...or death from progressive disease.” from the end of the first sentence.
- Section 11.2.2 Severity/Intensity (page 53). Corrected version of CTCAE and added CTCAE link.

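### Duration of response counts death as an event, then censors responders who die without documented progression; PFS has the same conflict for on-treatment deaths

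*Combined protocol and SAP*

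**What the plan says.** All the relevant text is in protocol Section 10.6.

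- **Duration of Response.** For responders only, it "is defined as time from the initial documented response (PR or better) to the first confirmed PD or until death from any cause". The sentence that follows reads: "Subjects without documented progression will be censored at the time of their last response assessment".
- **Progression-free Survival.** The clock runs from start of treatment to PD "or death from any cause on study treatment, whichever comes first". The section then says: "Subjects not experiencing a documented progression will be censored at the time of their last response assessment", with enrolment as the fallback date when there was no assessment.
- **Time to Progression.** "Time to progression will be calculated as the time from start of treatment until PD". Death is not an event here. The censoring sentence is the same as for PFS.
- **Overall Survival.** Censoring applies only where no death is recorded.

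On method, the section states: "The Kaplan-Meier procedures will be used to characterize the time-to-event curves (PFS, OS, TTP, and response duration". A median and 95% confidence interval are reported for each. No hypothesis test is attached to DoR or PFS.

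**The concern.** A progression-only censoring sentence suits TTP, where progression is the only event. It does not suit an endpoint that also counts death. In DoR and PFS it meets the event definition head on for one kind of subject: the one who dies without documented progression. That subject has an event at death by the first sentence and is censored before death by the second.

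Two programmers could each follow the text and produce different DoR and PFS curves from the same data. If the censoring sentence wins, deaths without progression are treated as uninformative drop-out. The reported DoR then describes progression alone, although it is defined as progression or death.

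The case can arise in practice. Under the Table of Events, scheduled response assessment ends at the treatment discontinuation visit, while survival status is collected every 3 months for up to 5 years after the last enrolment in the cohort. Deaths of responders who left treatment without progression would therefore be on the database, and Section 10.6 updates DoR at the end of that follow-up.

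**Working it through.** The plan states no event count, power or precision for DoR, so there is no figure to reproduce. The check has a logical part and an illustrative part.

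**1. Responder outcomes under the two DoR sentences**

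| Outcome | Event sentence | Censoring sentence |
|---|---|---|
| Confirmed PD | Event at PD | Not censored: agrees |
| Alive, no PD | No event | Censored at last assessment: agrees |
| Died, no documented PD | Event at death | Censored at last assessment: **conflict** |

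A death after PD is never the first event, so the third row is the only place where the death clause can operate. Applied literally, the censoring sentence cancels that clause completely and leaves PD as the only event.

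**2. PFS against TTP.** In Section 10.6 both start at start of treatment and carry the same censoring sentence. They differ only in that PFS adds deaths on study treatment. If those deaths are censored, the two endpoints are identical in the ITT population, although Section 3.2 lists them separately.

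**3. Size for DoR.** Let s be the share of first DoR events that are deaths without documented PD. The documents do not give s, so 0% to 30% is an assumption. Assume constant hazards and a death soon after the last assessment. With true median m, the total hazard is ln 2 / m. Censoring the deaths leaves hazard (1 − s) × ln 2 / m, so the reported median is m / (1 − s). For scale, m = 7.7 months, the median DoR quoted in Section 1.2 for POM+LD-dex in study CC-4047-MM-002.

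| s | 1/(1 − s) | Reported median (months) |
|---|---|---|
| 0% | 1.00 | 7.7 |
| 5% | 1.05 | 7.7/0.95 = 8.1 |
| 10% | 1.11 | 7.7/0.90 = 8.6 |
| 20% | 1.25 | 7.7/0.80 = 9.6 |
| 30% | 1.43 | 7.7/0.70 = 11.0 |

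**4. Check by simulation.** Kaplan-Meier medians were simulated with the same hazards, 28-day assessments and 12 to 36 months of follow-up. With deaths as events the median was 8.28 months in every scenario. It exceeds 7.7 because PD is seen only at the next visit. With deaths censored it was 8.28, 8.28, 9.20, 10.12 and 11.04 months for s = 0, 5, 10, 20 and 30%. The visit grid hides the effect at 5% and shows it from 10%.

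**5. A small invented example.** Ten responders: PD at 4, 6, 8, 10 and 12 months; deaths without PD at 5 and 7 (last assessments 4.6 and 6.4); three ongoing at 14.
- Deaths as events: the curve falls 0.9, 0.8, 0.7, 0.6, 0.5, so the median is 8 months.
- Deaths censored: 0.9, then × 7/8 = 0.79 at 6, × 5/6 = 0.66 at 8, × 4/5 = 0.53 at 10, × 3/4 = 0.39 at 12, so the median is 12 months.

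**6. How many subjects.** With the response rates assumed in Section 10.3 and the cohort sizes in Section 7.1, expected responders are 0.30 × 56 ≈ 17 (A), 0.70 × 112 ≈ 78 (B) and 0.60 × 20 = 12 (C). These are the DoR analysis sets. Even if every responder eventually had an event, a 5% to 30% share would put about 1 to 5, 4 to 24 and 1 to 4 subjects in conflict; at 0% there are none.

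**The case against.** The strongest reply is that no experienced analyst would read the text this way. DoR names death from any cause as an endpoint, PFS says whichever comes first, and censoring ordinarily means no event has occurred. On that reading nothing is overstated. The amendment log also records death being added to the DoR event sentence and death from progressive disease being removed from TTP, so the intent looks clear. All of this stands as evidence of intent. It does not remove the conflict, because nothing in the supplied text says which sentence governs: the Protocol Summary's efficacy overview addresses only time origins, and the opening of Section 10.6 sets no order of precedence. Section 4.4 refers to a Statistical Analysis Plan, but no separate censoring rules appear in the text available here.

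A reader might infer more than the documents support:

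- *That DoR will be overstated.* This holds only if the censoring sentence is the one programmed.
- *That DoR becomes the protocol's TTP.* Only the event set would match. DoR starts at response and covers responders; TTP starts at treatment.
- *That every death, or all 17, 78 and 12 responders, is affected.* Only responders who die without earlier documented PD are.
- *That the DoR percentages apply to PFS.* PFS counts only deaths on study treatment, so fewer deaths are in conflict, and the documents give no share for them.
- *That the log proves a drafting slip.* It describes superseded text, and its silence on the censoring sentence proves nothing.

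**Conclusion.** The conflict is real, and the supplied text does not resolve it. In DoR it concerns responders who die without documented PD; in PFS, subjects who die on study treatment without PD. If the event definitions govern, there is no bias. If the censoring sentences are applied literally, the death component is lost, PFS coincides with TTP in the ITT population, and the DoR median is overstated by nothing at a death share of 0%, 5% at 5%, 11% at 10%, 25% at 20% and 43% at 30%.

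Those figures rest on constant hazards, an assumed share, and deaths that follow soon after the last assessment. Where a responder stops treatment without PD and dies much later, censoring also removes event-free time, so the size could differ. No size is claimed for PFS.

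Both endpoints are secondary and descriptive, so ORR, power and type I error are unaffected. The point is worth settling before analysis, so that the rule is not chosen after the data are seen.

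**What to change.** In Section 10.6:

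- **Duration of Response.** Replace the censoring sentence with: *Responders with neither confirmed PD nor death will be censored at their last response assessment.*
- **Progression-free Survival.** Change the subject of the censoring sentence to: *Subjects with neither documented PD nor a death counted as an event under this definition*. Keep the rest, including the enrolment fallback. This wording leaves open the separate question of which deaths PFS should count.
- **Time to Progression.** No change.

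The cost is one sentence in each of two definitions and no new data, since survival status is already collected. The downside is that reported medians may be slightly shorter than under the literal censoring rule. If a separate analysis plan already gives precedence to the event definition, the edit simply brings the protocol into line with it.
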